### 9.1.2. Secondary endpoints

- OS from the start of the chemotherapy used in 1st line: time between the first injection of the chemotherapy used in 1st line and the date of death from any cause.
- PFS1: time between the first injection of avelumab and the date of progression or death from any cause. Progression status will be defined according to RECIST 1.1.
- PFS2: time between the first injection of avelumab and the date of progression or death from any cause during the 2nd line of treatment post-avelumab. Progression status will be defined according to RECIST 1.1.
- ORR: proportion of patients with a Complete Response or Partial Response as a best response during the avelumab treatment. Responses to treatment will be defined according to RECIST 1.1.
- DOR: time between the beginning of the response and progression or death from any cause.
- DOT: time between the first and last dose of avelumab.
- Patterns of progression under avelumab: metastatic sites and type of progression (new lesion(s)/progression of known lesion(s)).
- Subsequent treatments and response to these treatments: DOT, PFS, ORR and OS.
- Safety: AEs of any type, grade 3-4 AEs, AEs leading to interruption or discontinuation, AEs leading to death.

090177e1a41aac13\Final\Final On: 28-Jul-2025 13:50 (GMT)

- Premedications (acetaminophen and antihistamine): Proportion of patients who received a premedication at each injection of avelumab. Median number of cycles with premedication. To evaluate the correlation between infusion-related reactions and premedication.
- Evolution of PROs NCCN/FACT FBISI-18 and EQ-5D-5L scores during avelumab treatment.

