Clinical Follow-up data	
 
• Avelumab administration               
 
. Date of each infusion, dose
 
. Use of premedication (acetaminophen and antihistamine)
 
 
 
• Tumoral response under avelumab               
 
. At inclusion (for retrospective data collection): tumoral evaluation (yes/no), best response since avelumab initiation, date of partial or complete response if so, date of progression if so with site(s) of progression and type (new or preexisting lesions).
 
. Tumoral evaluation since last visit (yes/no, date), response (partial remission, complete remission, progression, stable disease, not evaluable), site(s) of progression if so and type (new or preexisting lesions).
 
 
 
• ECOG if the patient is still on avelumab
 
• Avelumab discontinuation
 
	X		X

090177e1a41aac13\Final\Final On: 28-Jul-2025 13:50 (GMT)

	
 
. Temporary interruption(s) with reason and dates
 
. Permanent discontinuation with reason and date
 
• Subsequent treatments after avelumab discontinuation
 
. Regimen and dates start/discontinuation
 
. Best response, progression with date,
 
• Death with date and cause
 
• Lost to follow-up if so and date
 
• Date of withdrawal if so
 
			
Safety	Adverse events (see section 11)	X		X
Concomitant treatments	Corticosteroids/AIS/NSAIDs, sartans/ACE inhibitors, antibiotics, PPI, if the patient is still on avelumab	X		X
Patient reported outcome (PRO)	
Patients initiating avelumab after the start of the study will complete NCCN/FACT FBISI-18 and EQ-5D-5L questionnaires:
 
 
1) at the time of avelumab initiation (baseline)
 
2) at different time points after initiation if the patient is still treated with avelumab : 6 weeks, 3 months, every three months for up to 2 years, tumor progression if so
 
3) at avelumab discontinuation (whatever the reason is)
 
	X	X	X

\* In order to validate the type of variants, anonymized anatomical pathology reports of the patients concerned will be collected and reviewed by the steering committee.

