6 ENDPOINTS AND COVARIATES

6.1 EFFICACY/EFFECTIVENESS ENDPOINT(S)

6.1.1 Time-to-event endpoints

Variable	Role	Data source(s)	Operational definition
Overall Survival (OS)	Time to Event Outcome (primary endpoint)	Patient medical records and CRF	Time (month) from the first injection of avelumab to death, whatever the reason +1
Overall Survival 2	Time to Event Outcome (secondary endpoint)	Patient medical records and CRF	Time (month) from the first injection of the chemotherapy used in 1st line to death, whatever the reason +1
Progression Free Survival (PFS)	Time to Event Outcome (secondary endpoint)	Patient medical records and CRF	Time (month) from the first injection of avelumab to the date of progression or death from any cause +1.
Progression Free Survival (PFS) 2	Time to Event Outcome (secondary endpoint)	Patient medical records and CRF	Time (month) from the first injection of avelumab to the date of progression or death from any cause during the 2nd line of treatment post-avelumab +1.
Objective Response Rate (ORR)	Outcome (secondary endpoint)	Patient medical records and CRF	Proportion of patients with a Complete Response (CR) or Partial Response (PR) as a best response during the avelumab treatment.
Duration Of Response uber avelumab (DOR)	Time to Event Outcome (secondary endpoint)	Patient medical records and CRF	Time (month) from the beginning of the response to progression or death from any cause + 1.
Duration Of	Time to Event	Patient medical	Time (month) from the first to last dose of avelumab + 1.

PFIZER CONFIDENTIAL

CT24-WI-GL03-RF02 2.0 Non-Interventional Statistical Analysis Plan For Primary Data Collection Study

01-Jun-2020

Page 12 of 28

Treatment (DOT)	Exposure	records and CRF	
Patterns of progression under avelumab	Outcome (secondary endpoint)	Patient medical records and CRF	Description of metastatic sites and type of progression (new lesion(s)/progression of known lesion(s)).
OS of subsequent treatment	Time to Event Outcome (secondary endpoint)	Patient medical records and CRF	Time (month) from the first injection of avelumab-subsequent treatment to death, whatever the reason +1

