8.2.2.6 Duration of treatment (DOT)

DOT will be analyzed using a survival analysis, in the FAS, using the following table for censorship, and date of first study treatment intake as starting date.

Table 5: Event Date and Outcome for DOTs

Scenario	Date of Event/Censoring	Outcome
Permanent Treatment discontinuation	Discontinuation Date	Event
Death (whatever the cause)	Death Date	Event
No permanent discontinuation reported at the end of the study	Last News Date	Censored
Lost to follow-up or early permanent study discontinuation without stopping treatment	Last News Date	Censored

DOT will also be described by subgroup (See section 5.3 for subgroup definition).

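### Duration of treatment is defined as first to last dose of avelumab, but SAP Table 5 dates the event at permanent discontinuation or death, which is a different endpoint

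*SAP*

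**What the plan says.** The definition is the same in both documents. Protocol 9.1.2 has "DOT: time between the first and last dose of avelumab". The endpoint table in SAP 6.1.1 has "Time (month) from the first to last dose of avelumab + 1" and classes the variable as an exposure.

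The analysis rule is in SAP 8.2.2.6: "DOT will be analyzed using a survival analysis, in the FAS, using the following table for censorship". In that table (Table 5):

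- The first event row is "Permanent Treatment discontinuation", dated at the discontinuation date.
- The second event row is death from any cause, dated at death.
- Patients with "No permanent discontinuation reported at the end of the study" are censored at the date of last news, as are patients lost to follow-up while on treatment.

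The last dose appears in no row.

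On data, Table 2 in Protocol 9.3 collects "Date of each infusion, dose" for avelumab and, as a separate item, "Permanent discontinuation with reason and date". SAP 11.1.2 treats the date of last dose as a variable of its own, with its own imputation rule for the safety analyses.

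DOT of subsequent treatment follows the same pattern: first to last dose in SAP 6.1.1, discontinuation or death in Table 7 (SAP 8.2.2.11).

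**The concern.** A programmer who follows Table 5 will not produce the quantity defined in Protocol 9.1.2 and SAP 6.1.1. The two agree only if the recorded discontinuation date is the date of the last infusion and no patient dies before a discontinuation is recorded. Neither document says that this is so.

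DOT is a stated secondary estimate, reported overall and by subgroup. SAP 8.1.3 adds Cox hazard ratios for subgroup comparisons, so a gap that differs between subgroups could carry into those ratios. SAP 8.2.3 also describes treatment duration and exposure separately. Without one definition, the same report could carry two treatment durations that disagree.

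**Working it through.** **No figure to reproduce.** The documents give no expected DOT, no precision target for DOT and no typical interval between last dose and recorded discontinuation. The check is therefore a comparison of date rules, followed by an illustration on stated assumptions.

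**Step 1: the rules for one patient.** Let S be the first infusion, L the last infusion, X the recorded permanent discontinuation and D the death date.

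| Situation | Defined DOT (Protocol 9.1.2, SAP 6.1.1) | Table 5 duration | Excess |
|---|---|---|---|
| Permanent discontinuation | L − S | X − S | X − L |
| Death before a recorded discontinuation | L − S | D − S | D − L |
| Still on treatment, or lost to follow-up on treatment | no rule given | censored at last news | not comparable |

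No infusion can follow permanent discontinuation or death, so X − L ≥ 0 and D − L ≥ 0. For a patient with an event, the Table 5 duration is never shorter than the defined one. The added 1 in the definition cancels from the difference if it is applied to both.

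**Step 2: can the two dates be treated as one?** The eCRF holds infusion dates and the discontinuation date as separate items, and SAP 11.1.2 handles the last-dose date separately. No text equates them. Table 2 of Protocol 9.3 also records temporary interruptions with dates. No rule says which date applies when an interruption becomes permanent.

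**Step 3: illustrative size.** Inputs:

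- 600 patients (Protocol 9.5).
- Assumed: exponential time to last dose, with a median of 4, 6, 9 or 12 months.
- Assumed: administrative censoring spread evenly over 24 to 42 months.
- Assumed: a fixed gap from last dose to recorded discontinuation of 0, 14, 28 or 42 days.
- Assumed: 0, 10% or 20% of patients die before a recorded discontinuation. For them an exponential gap from last dose to death replaces the fixed gap, with a mean of 30 days in the 10% case and 60 days in the 20% case.

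The Kaplan-Meier median was computed twice in each of 200 simulated data sets per setting, once with the event at last dose and once by Table 5. The table gives the mean difference in months, Table 5 minus defined. A range shows the spread over the four assumed medians.

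| Gap | No such deaths | 10% deaths, mean 30 days | 20% deaths, mean 60 days |
|---|---|---|---|
| 0 days | 0.0 | 0.10–0.12 | 0.43–0.46 |
| 14 days | 0.46 | 0.51–0.52 | 0.80–0.82 |
| 28 days | 0.92 | 0.93 | 1.15–1.18 |
| 42 days | 1.38 | 1.34–1.35 | 1.52–1.54 |

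The first column can be checked by hand. A constant gap moves every event by the same amount, and censoring starts only at 24 months, beyond these medians. The median therefore moves by the gap itself: 14/30.4375 = 0.46, 28/30.4375 = 0.92 and 42/30.4375 = 1.38 months. The shift hardly depends on the assumed median DOT.

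**Step 4: subsequent treatment.** The definition and Table 7 conflict in the same way, but the data differ. For treatments after avelumab, Table 2 in Protocol 9.3 lists the regimen with start and discontinuation dates and no individual infusion dates. On the listed variables, the first-to-last-dose definition cannot be computed, whereas Table 7 can.

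**The case against.** The strongest defence is that Table 5 is a reasonable measure in itself. A survival analysis needs an event and a censoring rule, and time to permanent discontinuation or death is a workable exposure endpoint. The study has no hypotheses, all analyses are descriptive, and neither the primary endpoint nor the sample size depends on DOT. All of this stands. It limits the stakes and shows that there are two valid ways to repair the text. It does not make the definition and the rule agree.

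A reader might go further than the documents allow in four ways:

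- **That the reported DOT is too long.** The discontinuation date is undefined. If sites enter the last infusion date and nobody dies before a recorded discontinuation, the excess is zero. Only equal or longer is supported.
- **That the inflation is a known percentage.** An assumed gap over an assumed median gives, for example, 0.25/8 = 3% or 1.0/4 = 25%. Both terms of each ratio are assumptions, neither document states a dosing interval or an expected DOT, and the range leaves out zero.
- **That Table 5 alone counts time off drug.** First-to-last-dose duration also includes interruptions after which treatment resumes. Only the stretch after the last dose differs.
- **That Table 7 should be re-dated in the same way.** The listed variables do not supply a last dose for subsequent treatment.

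**Conclusion.** The point holds as an inconsistency between definition and analysis. As written, Table 5 estimates time to permanent discontinuation or death, not first-to-last-dose DOT. This follows from the text alone and needs no assumption. The direction for a patient with an event, equal or longer, needs only that no dose follows permanent discontinuation or death.

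The size is not determined by the documents. On the assumptions above, the median shifts by 0 to about 1.5 months. Deaths before a recorded discontinuation contribute about 0.1 to 0.45 months when there is no other gap. Death is the clearest route to a real difference, because the death date then replaces the last-dose date however sites record discontinuation.

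The stakes are low, since this is a descriptive secondary endpoint. It should still be corrected, because the reported estimate would otherwise not be the one the protocol defines.

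**What to change.** Choose one of two routes for avelumab and state it in the SAP:

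1. **Keep the definition.** In Table 5, date the event at the last recorded avelumab infusion, both for permanent discontinuation and for death on treatment. State one censoring date for patients still on treatment or lost to follow-up.
2. **Keep Table 5.** Redefine the endpoint in SAP 6.1.1 as time to permanent discontinuation or death, label it so in the outputs, and record the departure from Protocol 9.1.2.

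For subsequent treatment, change the SAP 6.1.1 definition to match Table 7 and leave Table 7 as it is.

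Under either route, define the discontinuation date once, including which date applies when an interruption becomes permanent. A treatment discontinuation date also censors PFS and DOR (Tables 2 and 4), so the definition serves those endpoints too.

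The cost is SAP wording and a small programming change. Avelumab infusion dates are already collected, so route 1 needs no new data. Under route 1, DOT will come out the same as or shorter than under Table 5 for patients with an event.

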6.1.2 Objective response rate (ORR)

Best response will be calculated with all available response assessments, from study treatment initiation to treatment discontinuation (included) or end of study if no discontinuation.

PFIZER CONFIDENTIAL

CT24-WI-GL03-RF02 2.0 Non-Interventional Statistical Analysis Plan For Primary Data Collection Study

01-Jun-2020

Page 13 of 28

For best response, the following order will be used (from better outcome to worst)
Complete Response (CR) > Partial Response (PR) > Stable Disease (SD) > Not Estimable (NE) > Progressive Disease (PD).

6.1.3 **FBISI-18 score**

NCCN-FACT FBISI-18 is an 18-item questionnaire filled by the participant. The response to each of the 18 questions is evaluated using a 5-point scale ranging from 0='Not at all' to 4='Very much'. For items negatively framed, scores will be reversed for analysis so that higher scores translate a good quality of life.

6.1.4 **EQ-5D-5L score**

A participant's score at a specific timepoint will then go from 0 (0=severely symptomatic) to 72 (asymptomatic). For each participant, a unique Health state score will be created by combining the answer given to each of the 5 dimensions. This score will thus be ranging from 11111 (no problems in any domain) to 55555 (severe problems). This score will be after converted into EQ-5D single utility index values anchored at 0 for death and 1 for perfect health, by applying a formula download from the EQ-5D official website, that essentially attaches values (also called weights) to each of the levels in each dimension.

6.2 **SAFETY ENDPOINTS**

Adverse events (AE) reported during the study will be coded using the MedDRA terminology (SOC and PT) with the most recent version of MedDRA.

6.3 **COVARIATES**

Refer to [5.3](#).

7 **HANDLING OF MISSING VALUES**

Unless otherwise specified, all data will be evaluated as observed, and missing data will not be imputed.

- The objective response will be the only endpoint with a formal imputation of missing data. Participants who do not have a post-baseline radiographic tumour assessment due to early progression, who receive anti-tumour therapies other than the study treatments prior to reaching a CR or PR, or who die, progress, or drop out for any reason prior to reaching a CR or PR will be counted as non-responders in the assessment of OR. Each participant will have an objective response status (0: no OR; 1: OR).
- Time-to-event endpoints will include the observation period before an event of interest or till the censoring date and therefore will be analysed on all participants included in the analysis set.

- Continuous longitudinal data will be analysed using a mixed model for repeated measures. Maximum likelihood estimates will be provided on all participants included in the analysis set without any imputation.

Missing dates or partially missing dates will be imputed conservatively for adverse events and prior/concomitant medications/procedures. Specific rules for handling of missing or partially missing dates for date of birth, adverse events, prior/concomitant medications/procedures, and diagnosis of urothelial carcinoma are provided in [11.1](#)

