#### Follow-up:

[figure not shown]
The last patient prospectively included will be followed for 2 years. All other patients will be followed until death or until the end of the follow-up of the last patient prospectively included.

Patients who started avelumab before the start of the study will be followed retrospectively, but also prospectively for those still alive at the beginning of the study.

Follow-up visits will be made during the course of regular visits and/or hospitalisations. No additional visits or examinations are required by the protocol, as the study is observational: follow-up and treatment modalities will be at the sole discretion of the participating physician. Clinical data will be collected every three months after the inclusion in the study and until death or the end of the study: 24 months after the inclusion of the last prospective patient. Patients initiating avelumab after the start of the study (prospective part of the study) will complete PRO questionnaires : 1) at the time of avelumab initiation, 2) at different time points after initiation if the patient is still treated with avelumab (6 weeks, 3 months, and every three months for up to 2 years, tumor progression if so), 3) and at avelumab discontinuation.

Number of sites: the study will be proposed to all sites participating to the ATU program, plus some additional centers expected to treat patients after the ATU period. Approximately 100 sites are expected to participate to the study.

Figure 1. Study design

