8.2.2.4 Objective response rate (ORR)

ORR will be described overall and by subgroup defined in section 5.3.

Participants who do not have a post-baseline radiographic tumor assessment due to early progression, who receive anti-tumor therapies other than the study treatments prior to reaching a CR or PR, or who die, progress, or drop out for any reason prior to reaching a CR or PR will be counted as non-responders in the assessment of OR. Each participant will have an objective response status (0: no OR; 1: OR). OR rate (ORR) is the proportion of participants with OR in the FAS.

ORR will be calculated along with the 2-sided 95% CI using the Clopper-Pearson method (exact CI for a binomial proportion as computed by default by the FREQ procedure using the EXACT option).

ORR will also be described by subgroup (See section 5.3 for subgroup definition).

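### ORR on avelumab has two derivations in the SAP that disagree when the first CR or PR is recorded after progression or another anti-tumour therapy, and DOR does not exclude such responses

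*SAP*

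**What the plan says.** **Through best response.** The endpoint table in SAP 6.1.1 defines ORR as: "Proportion of patients with a Complete Response (CR) or Partial Response (PR) as a best response during the avelumab treatment". SAP 6.1.2 gives the derivation: "Best response will be calculated with all available response assessments, from study treatment initiation to treatment discontinuation (included", or to the end of the study where avelumab is not stopped. The ranking, from best to worst, is "Complete Response (CR) > Partial Response (PR) > Stable Disease (SD) > Not Estimable (NE) > Progressive Disease (PD". Neither section closes the window at first progression or at the start of another anti-tumour therapy.

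**Through an objective response status.** SAP 7 and SAP 8.2.2.4 list participants who are non-responders. The list covers those with no post-baseline radiographic assessment because of early progression and those given another anti-tumour therapy before CR or PR. It ends: "or who die, progress, or drop out for any reason prior to reaching a CR or PR will be counted as non-responders". SAP 8.2.2.4 then computes the rate from that 0/1 status: "OR rate (ORR) is the proportion of participants with OR in the FAS".

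**DOR.** SAP 8.2.2.5 starts the clock at the date of first CR or PR and takes as an event a progression seen after that response. It does not say that the response must precede any progression.

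**Protocol.** Section 9.1.2 says "Responses to treatment will be defined according to RECIST 1.1" and adds nothing on scans after progression. Under Follow-up in section 9.1, "follow-up and treatment modalities will be at the sole discretion of the participating physician".

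**The concern.** An endpoint needs one rule that two programmers would code the same way. Here, a patient with progression followed by PR while still on avelumab is a responder by SAP 6.1.1 and 6.1.2, and a non-responder by SAP 7 and 8.2.2.4. SAP 3 plans yearly interim analyses for publication, so the choice could differ between reports without anyone having decided it.

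The choice has a direction. Following 6.1.2 can only add responders. It also affects DOR: the same patient is a PFS event at the progression date (SAP Table 2), yet could start a response duration later, with the earlier progression ignored.

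**Working it through.** The documents state no ORR, no precision target for ORR and no rate of response after progression. There is no plan figure to reproduce, so the check applies both rules to scan sequences and then shows what each assumed share of discordant patients would do.

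**Step 1. The two rules, both over the avelumab period**

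- Rule A (SAP 6.1.1 and 6.1.2): take the best of all scans; responder if CR or PR.
- Rule B (SAP 7 and 8.2.2.4): responder only if CR or PR comes before any progression. Another anti-tumour therapy works in the same way as progression.

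| Scans in order | Best response (6.1.2) | Rule A | Rule B |
|---|---|---|---|
| SD, PR, PD | PR | responder | responder |
| PD, PR | PR | responder | **non-responder** |
| SD, PD, CR | CR | responder | **non-responder** |
| PD, SD | SD | non-responder | non-responder |
| PD, NE | NE | non-responder | non-responder |
| PD | PD | non-responder | non-responder |

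The rules part only when the first CR or PR follows progression (or another therapy) on avelumab. Every rule B responder is also a rule A responder, so the difference cannot be negative.

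**Step 2. Can the sequence occur?** The protocol leaves treatment to the physician, and neither document requires avelumab to stop at progression. Protocol Table 2 collects tumour evaluations at each follow-up. This shows that the sequence is possible, not that it is common. SAP Table 2 has a row for progression before discontinuation, but that is an ordinary PFS event and says nothing about rescanning or later response.

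**Step 3. Size**

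Inputs: N = 600 (Protocol 9.1 and 9.5); Clopper-Pearson 95% CI (SAP 8.2.2.4). The discordant share d and the rule B ORR are assumptions.

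- Extra responders = d × N. For d = 1%: 0.01 × 600 = 6.
- Change in ORR = 6/600 = 1.0 point. With the 500 patients still given in SAP 2.1: 0.01 × 500 = 5, and 5/500 is again 1.0 point.

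With an assumed rule B ORR of 20% (0.20 × 600 = 120):

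| d (assumed) | Responders, rule A | ORR | 95% CI |
|---|---|---|---|
| 0 | 120 | 20.0% | 16.9 to 23.4 |
| 1% | 126 | 21.0% | 17.8 to 24.5 |
| 3% | 138 | 23.0% | 19.7 to 26.6 |
| 5% | 150 | 25.0% | 21.6 to 28.7 |

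The shift in points equals d whatever the base. With a rule B ORR of 10%, d = 1%, 3% and 5% give 11.0%, 13.0% and 15.0%; with 30%, they give 31.0%, 33.0% and 35.0%.

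**Step 4. DOR.** Take PD, then PR, then PD, all on avelumab. SAP Table 2 gives a PFS event at the first PD. SAP 8.2.2.5 read alone starts DOR at the later PR and counts the second PD as the event. If DOR were restricted to participants with a positive status under 8.2.2.4, this patient would not enter, but 8.2.2.5 names only the FAS and the date of first response.

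**The case against.** The best defence is that SAP 8.2.2.4 is the operative rule. Sections 6.1.1 and 6.1.2 give a general definition and a scan window; SAP 7 and 8.2.2.4 add specific exceptions, and a programmer working from 8.2.2.4 gets a single ORR. That is a fair way to reconcile the text, but the SAP does not say so, and DOR is not tied to the 8.2.2.4 status.

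A second defence is that SAP 7 presents its rule as imputation of missing data, so it might cover only participants who never reach CR or PR. The conflict would then vanish, with 6.1.2 governing. Against this, the rule turns on what happens before CR or PR, and 8.2.2.4 repeats it outside the missing-data section. The two defences also give opposite answers for the same patient, which shows that the precedence has to be stated.

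Naming RECIST 1.1 does not settle it from these documents: they do not spell out how it treats scans after progression, and the SAP writes its own window and ranking.

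Two stronger readings are tempting. A reader might infer that best response itself has two derivations. It has one, in 6.1.2; SAP 7 and 8.2.2.4 define a response status. A reader might also infer that progressors with a later SD or NE scan distort the results by leaving the PD category. They are non-responders under both rules, so ORR does not move, and neither 8.2.2.4 nor the summary in 8.2.5 lists a best-response distribution. The table shells are a separate file not available here.

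It is also true that ORR is secondary, that all analyses are descriptive (SAP 4.2), and that a 1-point shift sits well inside the confidence interval.

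**Conclusion.** The point stands in a narrow form: as written, the SAP gives ORR two derivations that disagree for one sequence, and it allows that sequence into DOR. The primary OS analysis is unaffected.

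The size is unknown. It is 1.0 point of ORR for each 1% of patients with the sequence, upward under 6.1.2, and zero if there are none. Only N = 600 comes from the documents; the shares of 1% to 5% and the base ORRs of 10% to 30% are assumptions. The documents do not support a claim that ORR will in fact be materially inflated. They show that it could be raised by a choice that the plan leaves open.

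**What to change.** In SAP 6.1.2, limit the assessments to those from the first avelumab dose up to and including the earliest of first documented progression, start of another anti-tumour therapy, or avelumab discontinuation, or to end of study if none of these occurs. State that ORR in 6.1.1 and 8.2.2.4, and the DOR start in 8.2.2.5, use this same window. The non-responder text in SAP 7 then agrees with it.

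For retrospective patients, whose best response is entered as a summary, compare the recorded CR or PR date with the recorded progression date; Protocol Table 2 collects both. That table lists anti-cancer regimens after avelumab only under subsequent treatments following discontinuation, so the other-therapy limb applies where a start date is available. List responses after the window separately, so that nothing observed is lost.

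The cost is a short wording change and a date comparison in the programs, with no new data collection and no effect on patient care. The downside is that ORR may come out slightly lower than under 6.1.2 as it stands.
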